6.2.2. Treatment Persistence

Persistence with B/F/TAF

- Persistence with B/F/TAF at Week 12 is defined as having received B/F/TAF for \geq 57 days (i.e. the lower bound of the Week 12 visit window) and will be calculated as the proportion of participants remaining on B/F/TAF within the Week 12 analysis visit window in the FAS. Participants who prematurely discontinued from the study drug and then started the post ARV and have received B/F/TAF (including study and commercial drugs) for \geq 57 days are considered as persistence with B/F/TAF at Week 12.

- Persistence with B/F/TAF at Week 24 is defined as having received B/F/TAF for ≥ 127 days (i.e. the lower bound of the Week 24 visit window) and will be calculated as the proportion of participants remaining on B/F/TAF within the Week 24 analysis visit window in the FAS. Participants who prematurely discontinued from the study drug and then started the post ARV and have received B/F/TAF (including study and commercial drugs) for ≥ 127 days are considered as persistence with B/F/TAF at Week 24.

Non-persistence with B/F/TAF

- Non-persistence with B/F/TAF at Week 12 will be calculated as the proportion of participants who prematurely discontinue B/F/TAF by Weeks 12 Visit (ie, prematurely discontinued B/F/TAF and having received B/F/TAF for < 57 days) in the FAS.
- Non-persistence with B/F/TAF at Week 24 will be calculated as the proportion of participants who prematurely discontinue B/F/TAF by Weeks 24 Visit (ie, prematurely discontinued B/F/TAF and having received B/F/TAF for < 127 days) in the FAS.

Treatment persistence and non-persistence will be summarized. Their 2-sided 95% CIs of the proportion will be constructed based on the Clopper-Pearson exact method.

Reason for B/F/TAF premature discontinuation during the study will be listed.

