## 2. OBJECTIVES AND ENDPOINTS

Primary Objective	Co-Primary Endpoints

To assess the safety of switching to B/F/TAF in virologically suppressed participants unable/unwilling to continue on CAB+RPV IM injections or wishing to switch to oral therapy through Week 12

	

Proportion of participants experiencing treatment-emergent Grade 3 or 4 study drug-related adverse events through Week 12

Proportion of participants experiencing treatment-emergent Grade 3 or 4 laboratory abnormalities through Week 12

Secondary Objectives	Secondary Endpoints

To assess the pharmacokinetics of BIC, CAB, and RPV after switching to B/F/TAF from CAB+RPV

To assess the efficacy and persistence of B/F/TAF after switching from CAB+RPV

To assess the safety of B/F/TAF after switching from CAB+RPV through Week 24

To evaluate treatment satisfaction of switching to B/F/TAF from CAB+RPV

	

Plasma concentrations of BIC, CAB, and RPV at Day 1, Weeks 4, 12, and 24, as appropriate

Proportion of participants with HIV-1 RNA <math>\geq 50</math> copies/mL at Weeks 12 and 24 (missing = excluded and discontinuation = failure)

Number and proportion of participants with B/F/TAF discontinuation by Weeks 12 and 24

Proportion of participants experiencing treatment-emergent grade 3 or 4 laboratory abnormalities through Week 24

Change in HIV treatment satisfaction (HIVTSQc) score at Week 4

Exploratory Objective	Exploratory Endpoints

To understand PWH experience with injectable and oral therapies for HIV treatment

To evaluate reasons for switching to B/F/TAF from CAB+RPV

	

Participant reported experiences with CAB+RPV, preferences for injectable and oral therapies

Participant-reported reasons for switching to B/F/TAF

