#### **8.5. Efficacy Analysis**

The analysis of the efficacy endpoints will be based on the FAS. The proportion of participants with HIV-1 RNA  $\geq$  50 copies/mL at Weeks 12 and 24, and the proportion of participants with HIV-1 RNA  $<$  50 copies/mL at Weeks 12 and 24 as determined by M=E and D=F approaches will be summarized using descriptive statistics. Their 2-sided 95% CIs of the proportion will be constructed based on the exact method.

The proportion of participants who prematurely discontinued B/F/TAF through Weeks 12 and 24 and their 95% CIs will be summarized similarly.

The change from baseline in CD4+ cell counts and percentages will be summarized by visit using descriptive statistics.

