4.2.1. Duration of Exposure to Study Drug

Total duration of exposure to study drug will be defined as last dosing date minus first dosing date plus 1, regardless of any temporary interruptions in study drug administration, and will be expressed in weeks using up to 1 decimal place (eg, 4.5 weeks). If the last study drug dosing date is missing, the latest date among the study drug end date, clinical visit dates, laboratory sample collection dates, and the vital signs assessment dates that occurred during the on-treatment period will be used for that participant included in the final analyses.

The duration of exposure to study drug will be summarized using descriptive statistics (n, mean, SD, median, Q1, Q3, minimum, and maximum) and as the number and percentage of participants exposed for specified periods, eg, \geq 4 weeks (28 days), \geq 8 weeks (56 days), \geq 12 weeks (84 days), \geq 24 weeks (168 days), etc.

Summaries will be provided by overall participants for the Safety Analysis Set.

No formal statistical testing is planned.

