6.4. Change From Protocol-Specified Efficacy Analyses

There are no deviations from the protocol-specified efficacy analyses.

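### The persistence endpoint counts premature stops only before Day 57 (Week 12) or Day 127 (Week 24), so later stops in each period are reported as persistent

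*SAP*

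**What the plan says.** Protocol Section 2 lists as a secondary endpoint "Number and proportion of participants with B/F/TAF discontinuation by Weeks 12 and 24", under an objective that names persistence. Protocol 8.5 plans to report "The proportion of participants who prematurely discontinued B/F/TAF through Weeks 12 and 24" with 95% confidence intervals. Neither section sets a cut-off earlier than the named week.

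SAP 6.2.2 first describes non-persistence as premature discontinuation by the Week 12 or Week 24 visit. It then spells this out as "prematurely discontinued B/F/TAF and having received B/F/TAF for < 57 days" for Week 12 and "prematurely discontinued B/F/TAF and having received B/F/TAF for < 127 days" for Week 24. Persistence is at least 57 or at least 127 days of drug, the second figure being explained as "the lower bound of the Week 24 visit window". Someone who stopped study drug prematurely but reached that many days, on study or commercial supply, is expressly counted as persistent. Both proportions get Clopper-Pearson intervals.

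SAP Table 3-1 gives Week 12 a nominal Day 84 with a window of Days 57 to 126, and Week 24 a nominal Day 168 with a window of Days 127 to 210. SAP 6.4 states: "There are no deviations from the protocol-specified efficacy analyses".

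**The concern.** An analysis window decides which scheduled visit an observation belongs to when visits drift from their planned day. The date of last dose needs no such allocation, and the start of a window is not the end of 12 or 24 weeks of treatment. Used as a cut-off, it leaves the final part of each period uncounted.

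Take a participant who takes drug daily and stops prematurely on Day 130. The disposition table (SAP 4.1) shows a premature discontinuation of study drug. The exposure table (SAP 4.2.1) shows less than 24 weeks. The persistence table shows a participant persistent at Week 24. A reader will take that last label literally.

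Persistence on B/F/TAF after leaving injectable therapy is a named secondary objective. The rule can only make it look better, and the confidence interval inherits the same shift.

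**Working it through.** **Inputs.** Nominal days 28, 84 and 168, and the windows, from SAP Table 3-1. Cut-offs 57 and 127 from SAP 6.2.2. Visit windows of ±2 days through Week 12 and ±6 days at Week 24 from footnote c of protocol Table 3. About 35 participants from protocol 8.9. Clopper-Pearson intervals from SAP 6.2.2. The documents give no expected B/F/TAF discontinuation rate, so the rates in step 4 are assumptions.

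**1. Reproduce the cut-offs.** Each window starts one day after the midpoint of adjacent nominal days.
- Week 12: (28 + 84)/2 + 1 = 57
- Week 24: (84 + 168)/2 + 1 = 127

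Both match Table 3-1 and SAP 6.2.2.

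**2. Uncounted span**, taking uninterrupted dosing so that days of drug equal study days.
- Week 12: 84 − 57 + 1 = 28 days; 28/84 = 33.3%
- Week 24: 168 − 127 + 1 = 42 days; 42/168 = 25.0%

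These include the nominal day itself; without it the spans are 27 and 41 days.

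**3. Does visit timing require such early cut-offs?** The earliest in-window visits are Day 84 − 2 = 82 and Day 168 − 6 = 162. The cut-offs fall 82 − 57 = 25 and 162 − 127 = 35 days before them. Visit scheduling does not explain the gap.

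**4. Illustration under a constant hazard.** Let p be the true proportion stopping by Day 168. The rule counts last doses through Day 56 or Day 126.
- Week 24 counted: 1 − (1 − p)^(126/168)
- Week 12 true: 1 − (1 − p)^(84/168)
- Week 12 counted: 1 − (1 − p)^(56/168)

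| Assumed p | Week 24 true | Week 24 reported | Week 12 true | Week 12 reported |
|---|---|---|---|---|
| 0.05 | 5.0% | 3.8% | 2.5% | 1.7% |
| 0.10 | 10.0% | 7.6% | 5.1% | 3.5% |
| 0.20 | 20.0% | 15.4% | 10.6% | 7.2% |

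With c the counted Week 24 proportion, the expected Week 24 undercount in 35 participants is 35 × (p − c), about 0.4, 0.8 and 1.6 people. The chance that at least one stop is missed is 1 − [1 − (p − c)]^35 = 35%, 57% and 81%.

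**5. Effect on the reported interval, n = 35.** One participant is 1/35 = 2.9 points.
- Four stops by Week 24, one of them on Day 130: SAP rule 3/35 = 8.6% (95% CI 1.8 to 23.1); counting through Day 168, 4/35 = 11.4% (3.2 to 26.7).
- Two stops, both after Day 127: SAP rule 0/35 (0 to 10.0); counting through Day 168, 2/35 = 5.7% (0.7 to 19.2).

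**The case against.** The best defence is consistency within the SAP. The discontinuation-equals-failure analysis in SAP 6.2.1 uses the same lower bound to decide who failed by discontinuing, and 6.2.2 follows it openly with the day limits printed. The protocol attaches no day number to Weeks 12 and 24 and leaves detail to the SAP. Late stops are not hidden either: disposition, the listing of reasons and the exposure categories all show them.

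Parts of this stand.
- Stops after 57 to 84 days are missed at Week 12 but are below 127 days, so they enter the Week 24 proportion. Only stops after 127 to 168 days escape both.
- Under SAP 3.7.1 a missing last-dose date is imputed from the latest drug, clinic or laboratory date. No visit is scheduled between Weeks 12 and 24, so someone lost after Week 12 with no later record would be placed near Day 84 and counted at Week 24. The gap mainly affects stops with a recorded last dose after Day 126, and step 4 of the working is an upper picture to that extent.
- Disposition, exposure and persistence measure different things. The exposure comparison is the weaker one, because a completer whose last dose is on Day 162 also has fewer than 168 days.
- The study is descriptive, and the intervals in the first example of step 5 overlap heavily.

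None of this supports the cut-offs. The analysis in 6.2.1 classifies an HIV-1 RNA result within a window, whereas persistence concerns the date treatment stopped. Visibility in other tables does not correct the endpoint proportion or its interval. SAP 6.2.2 also contradicts itself by describing the event as stopping by the Week 24 visit and then ending the count at least 35 days before the earliest in-window visit.

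**Conclusion.** The concern holds. As written, SAP 6.2.2 does not estimate discontinuation by or through Weeks 12 and 24, and SAP 6.4 does not declare the change. The uncounted spans, 33% of the Week 12 period and 25% of the Week 24 period, follow from the SAP's own days. They assume only uninterrupted dosing, since SAP 6.2.2 does not say how gaps are treated. The direction is fixed: discontinuation is understated and persistence overstated.

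The size in the actual data depends on how many participants stop late. It is nil if none do and 2.9 points for each one who does. The rates in the illustration are assumptions. The weight is that of a descriptive secondary endpoint.

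**What to change.** In SAP 6.2.2, define non-persistence at Week 12 (Week 24) as premature discontinuation on the Study Drug Completion eCRF with the last B/F/TAF dose before the Week 12 (Week 24) visit date, or before Day 84 (Day 168) if that visit did not take place. Define persistence as the complement. The provision for commercial B/F/TAF can stay, with the same limits applied to the last dose from either supply. Working from the last-dose date also settles how temporary interruptions are handled.

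In-window completers are not miscounted. Someone finishing on Day 162 did not stop prematurely and remains persistent.

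The discontinuation-equals-failure rule in SAP 6.2.1 can keep its window bound. A footnote should then say that its discontinuation row and the persistence table use different cut-offs. If the sponsor keeps Days 57 and 127 for persistence, the least that is needed is to declare the departure in SAP 6.4 and report the count through the nominal weeks beside it.

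The cost is a paragraph of SAP text and one derivation, from last-dose dates and completion status already collected. SAP Section 1 places SAP finalisation before database finalisation, so the change belongs there. The persistence figure may become slightly less favourable.

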6.3. Analysis of the Additional Efficacy Endpoints

6.3.1. Analysis of CD4 Cell Counts and CD4 Percentages

The change from baseline in CD4 cell counts and CD4 percentages will be summarized by visit for participants in the FAS based on observed, on-treatment data (ie, data collected up to 1 day after the last dose date of B/F/TAF) using descriptive statistics.

The mean and 95% CI of change from baseline in CD4 cell count over time will be plotted using observed data for the FAS.

6.4. Change From Protocol-Specified Efficacy Analyses

There are no deviations from the protocol-specified efficacy analyses.

7. SAFETY ANALYSES

Safety data collected up to 30 days after permanent discontinuation of B/F/TAF study drug will be summarized for the participants in the Safety Analysis Set, unless specified otherwise. All safety data will be included in the data listings.

7.1. Safety Endpoints

The co-primary endpoints of this study are:

- Proportion of participants experiencing treatment-emergent Grade 3 or 4 study drug-related adverse events (AEs) through Week 12
- Proportion of participants experiencing treatment-emergent Grade 3 or 4 laboratory abnormalities through Week 12.

The secondary safety endpoints of this study are:

- Proportion of participants experiencing treatment-emergent Grade 3 or 4 study drug-related adverse events (AEs) through Week 24
- Proportion of participants experiencing treatment-emergent grade 3 or 4 laboratory abnormalities through Week 24.

7.2. Adverse Events and Deaths

7.2.1. Adverse Events Dictionary

Clinical and laboratory adverse events (AEs) will be coded using the current version of MedDRA. System organ class (SOC), high-level group term (HLGT), high-level term (HLT), preferred term (PT), and lowest-level term (LLT) will be provided in the AE dataset.

7.2.2. Adverse Event Severity

Adverse events are graded by the investigator or qualified sub-investigator as Grade 1, 2, 3, 4, or 5 according to Division of AIDS (DAIDS) Toxicity Grading Scale, Version 2.1. For each episode, the highest grade attained should be reported as defined in the Toxicity Grading Scale. The severity grade of events for which the investigator did not record severity will be categorized as “missing” for tabular summaries and data listings. The missing category will be listed last in summary presentation.

7.2.3. Relationship of Adverse Event to Study Drug

Related AEs are those for which the investigator selected “Related” on the AE CRF to the question of “Related to Study Treatment.” Relatedness will always default to the investigator’s choice, not that of the medical monitor. Events for which the investigator did not record relationship to study drug will be considered related to study drug for summary purposes. However, by-participant data listings will show the relationship as missing.

7.2.4. Relationship of Adverse Events to Study Procedures

Study procedure related AEs are those for which the investigator selected “Yes” on the AE case report form (CRF) to the question of “Related to Study Procedures.” Relatedness will always default to the investigator’s choice, not that of the medical monitor. Events for which the investigator did not record relationships to study procedure will be considered related to study procedure for summary purposes. However, by-participant data listings will show the relationship as missing.

7.2.5. Serious Adverse Events

An SAE is defined as an event that, at any dose, results in the following:

- Death
- A life-threatening situation (Note: the term “life-threatening” in the definition of “serious” refers to an event in which the participant was at risk of death at the time of the event; it does not refer to an event that hypothetically might have caused death if it were more severe.)
- In-patient hospitalization or prolongation of existing hospitalization.
- Persistent or significant disability/incapacity.
- A congenital anomaly/birth defect.
- A medically important event or reaction: such events may not be immediately life – threatening or result in death or hospitalization but may jeopardize the participant or may require intervention to prevent 1 of the other outcomes constituting SAEs. Medical and scientific judgment must be exercised to determine whether such an event is reportable under expedited reporting rules. Examples of medically important events include intensive treatment in an emergency room or at home for allergic bronchospasm; blood dyscrasias or convulsions that do not result in hospitalization; and development of drug dependency or drug abuse.

Serious adverse events (SAEs) will be identified and captured as SAEs if the AEs met the definitions of SAEs that were specified in the study protocol. SAEs captured and stored in the clinical database will be reconciled with the SAE database from the Gilead Global Patient Safety Department before data finalization.

7.2.6. Treatment-Emergent Adverse Events

7.2.6.1. Definition of Treatment-Emergent Adverse Events

Treatment-emergent adverse events (TEAEs) are defined as:

- Any AEs with onset date on or after the study drug start date and no later than 30 days after the study drug stop date; or
- Any adverse event leading to study drug discontinuation.

7.2.6.2. Incomplete Dates

If the start date of the AE is incomplete and the AE stop date is not prior to the first dosing date of study drug, then the month and year (or year alone if month is not recorded) of start determine whether an AE is treatment emergent. The event is considered treatment emergent if both of the following 2 criteria are met:

- The AE start date is the same as or after the month and year (or year) of the first dosing date of study drug, and
- The AE start date is the same as or before the month and year (or year) of the date corresponding to 30 days after the date of the last dose of study drug.

An AE with completely missing start and stop dates, or with the start date missing and a stop date later than the first dosing date of study drug, will be considered treatment emergent. In addition, an AE with the start date missing and incomplete stop date with the same or later month and year (or year alone if month is not recorded) as the first dosing date of study drug will be considered treatment emergent.

7.2.7. Summaries of Adverse Events and Deaths

Treatment-emergent AEs will be summarized based on the Safety Analysis Set.

7.2.7.1. Summaries of AE incidence in Combined Severity Grade Subsets

- A brief, high-level summary of the number and percentage of participants who experienced at least 1 TEAE during the study (ie, through Week 24) in the categories described below will be provided. All deaths observed in the study will also be included in this summary.
- In addition, a brief, high-level summary of TEAEs up to the nominal Week 12 visit will be provided. Any TEAE onset date was on or before the nominal Week 12 visit date will be included.

- If TEAE onset date is partial, the onset date is on or before the month and year (or year alone) of nominal Week 12 visit, will be included as on or before nominal week 12. If the TEAE onset date is completely missing, will be included as well.
- If participants discontinued the study before Week 12 visit, all TEAEs will be included.

The number and percentage of participants who experienced at least 1 TEAE will be provided and summarized by SOC, HLT (if applicable), PT as follows:

- TEAEs during the whole study period (ie, through Week 24)
- TEAEs up to the nominal Week 12 visit (ie, through Week 12).
- For the AE categories described below, summaries will be provided by SOC and PT as follows for (i) the whole study period (ie, through Week 24), and (ii) up to the nominal Week 12 visit (ie, through Week 12).
- TEAEs with Grade 3 or higher
- TE treatment-related AEs
- TE treatment-related AEs with Grade 3 or higher
- TE SAEs
- TE treatment-related SAEs
- TEAEs leading to premature discontinuation of study drug
- TEAEs leading to premature discontinuation of study.

Multiple events will be counted only once per participant in each summary. Adverse events will be summarized and listed first in alphabetic order of SOC (and HLT within each SOC if applicable), and then by PT in descending order of total frequency within each SOC. For summaries by severity grade, the worst severity will be used for those AEs that occurred more than once in an individual participant during the study.

In addition to the above summary tables, all TEAEs, TE SAEs, TE treatment-related AEs, and TE treatment-related SAEs will be summarized by PT only, in descending order of total frequency.

In addition, data listings will be provided for the following:

- All AEs, indicating whether the event is treatment emergent,
- All AEs up to nominal Week 12 visit, indicating whether the event is treatment emergent

- All AEs with severity of Grade 3 or higher
- All SAEs
- All treatment-related AEs
- All Deaths
- All SAEs leading to death (i.e., outcome of death)
- All AEs leading to premature discontinuation of study drug
- All AEs leading to premature discontinuation of study.

7.2.8. Additional Analysis of Adverse Events

7.3. Laboratory Evaluations

Laboratory data collected during the study will be analyzed and summarized using both quantitative and qualitative methods. The analysis will be based on values reported in conventional units. When values are below the LOQ, they will be listed as such, and the closest imputed value will be used for the purpose of calculating summary statistics as specified in Section 3.7.

Summaries of laboratory data will be provided for the Safety Analysis Set and will include data collected up to the date of the last dose of study drug plus 30 days.

A by-participant listing for laboratory test results will be provided by participant ID number and visit in chronological order for hematology, serum chemistry, and urinalysis separately for all data collected during the study. Values falling outside of the reference range and/or having a severity grade of 1 or higher on the Gilead Grading Scale for Severity of Adverse Events and Laboratory Abnormalities will be flagged in the data listings, as appropriate. The listing will include derived visit information of the study (ie, derived visit and study day).

No formal statistical testing is planned on laboratory data.

